6.0 Investigational Plan

6.1 Overall Study Design and Plan: Description

This is a multicenter, randomized, double-blind, placebo-controlled study to evaluate the safety and efficacy of 3 dose levels (0.25, 0.5, and 1 mg) of oral CR845 in moderate-to-severe CKD patients with moderate-to-severe pruritus.

This study will consist of a Screening Period, a 7-day Run-in Period, a 12-week Treatment Period, and a Follow-up Visit (approximately 7 to 10 days after the last dose of study drug). Informed consent will be obtained prior to performing any study-specific procedures. Screening will occur within 7 to 28 days prior to randomization to assess eligibility.

Eligible patients will complete a 7-day Run-in Period during the week prior to randomization when they will be required to complete at least 4 Worst Itching Intensity numerical rating scale (NRS) worksheets. The mean baseline Worst Itching Intensity NRS score during the 7-day Run-in Period must be ≥ 5 . The mean baseline is defined as the average of all non-missing scores reported from the start of the 7-day Run-in Period. For consistency, patients will be requested to complete the Worst Itching Intensity NRS worksheets at a similar time each day.

Patients will also be trained on the Skindex-10 Scale, 5-D Itch Scale, Patient Global Impression of Worst Itch Severity, and Patient Global Impression of Change (PGIC) worksheets at any time during the Run-in Period or on Day 1 of the Treatment Period.

Day 1 of the Treatment Period will be defined as the day of the administration of the first dose of study drug.

[figure not shown]
If patients continue to meet all inclusion and no exclusion criteria at the end of the 7-day Run-in Period, they will be randomized in a 1:1:1:1 ratio to receive orally once daily either placebo or CR845 tablets at doses of 0.25, 0.5 or 1 mg. Randomization will be stratified according to the patient's renal disease status: moderate CKD; severe CKD non-dialysis; severe CKD on dialysis (ie, 3 categories). The randomization of severe CKD patients on hemodialysis will be capped at approximately 20% of the total sample size (ie, 48 of 240 patients).

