6.5.1.1 Worst Itching Intensity Numerical Rating Scale

Intensity of itch will be measured using an NRS scale ([Appendix 2, Section 14.2](#)) on a worksheet on which patients will be asked to indicate the intensity of the worst itching they experienced over the past 24 hours by marking one of 11 numbers, from 0 to 10, that best describes it, where “0” is labeled with the anchor phrase “no itching” and “10” is labeled “worst itching imaginable.” Patients will be provided with these worksheets to record their 24-hour worst itching assessment scores.

The Worst Itching Intensity NRS has been widely utilized for evaluation of chronic itch, including uremic pruritus [[Kumagai 2010](#); [Pisoni 2006](#); [Mathur 2010](#); [Ständer 2013](#)].

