8.6 Efficacy Analyses

8.6.1 Primary Efficacy Endpoint

The primary efficacy endpoint is defined as the change from baseline to Week 12 of the Treatment Period with respect to the weekly mean of the daily 24 hour Worst Itching Intensity NRS score. The weekly mean of the 24-hour Worst Itching Intensity NRS score will be defined as the sum of the daily Worst Itching Intensity NRS score reported during a specific week during the Treatment Period (eg, Days 2 to 8, Days 9 to 15, Days 16 to 22, etc.) divided by the number of days with non-missing scores for that week. If the daily worst itching score is missing for >3 days during a specific week, the corresponding weekly mean worst itching score will be set to missing. The baseline score will be defined as the average of the daily 24-hour Worst Itching Intensity NRS scores over the last 7 days prior to randomization; at least 4 completed Worst Itching Intensity NRS worksheets will be required prior to randomization.

The primary efficacy variable will be analyzed using a mixed effects model with repeated measures (MMRM). The model will contain treatment, week, and treatment-by-week interaction as fixed effects; baseline score and renal disease status as covariates, and patient as a random effect. For each dose group, the treatment group difference vs placebo will be estimated as the simple contrast in the treatment effect at Week 12 of the Treatment Period.

An appropriate covariance matrix will be used to model the within patient errors. The use of an unstructured covariance matrix structure as well as other structures, such as spatial patterns, that require fewer parameters (Toeplitz, autoregressive, or compound symmetry) will be examined. The Akaike information criterion will be used to determine the appropriate covariance matrix for the MMRM model. The Kenward-Roger approximation will be used to estimate the denominator degrees of freedom.

In the primary efficacy analysis, missing NRS data will be imputed using a multiple imputation (MI) approach, assuming that patients who discontinue study drug early would have similar Worst Itching Intensity NRS scores as other patients in their respective treatment arm that have complete data. Specifically, the following steps will be followed:

- Intermittent missing NRS scores will first be imputed using the Markov Chain Monte Carlo (MCMC) method implemented with the SAS MI procedure, which is appropriate for non-monotonic missing data.

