4.3 Additional efficacy endpoint(s)

The additional efficacy endpoints of this study are:

Itch-intensity Measures

- Proportion of patients who have an improvement from baseline at each week of the Treatment period and end of treatment with respect to the weekly mean of the 24-hour Worst Itching Intensity NRS scores ≥ 1 , ≥ 2 , ≥ 3 (excluding week 12) and ≥ 4 points.
- Proportion of “complete responders” with respect to Worst Itching Intensity score NRS at each week of the Treatment period and at end of treatment. A patient that has $\geq 80\%$ of the non-missing daily NRS scores in a week equal to 0 or 1 is considered a complete responder at that week.
- Change from baseline in the weekly mean of the 24-hour Worst Itching Intensity NRS score at each week of the Treatment period (Week 1 to Week 11) and at end of treatment.
- Proportion of patients who rate their itch condition as “Very much improved” or “Much improved” at Week 12/end of treatment, as measured by the Patient Global Impression of Change (PGIC).

Statistical Analysis Plan (SAP)

- Proportion of patients in each of the 5 categories of the Patient Global Impression of worst itch severity at baseline and at each scheduled weekly visit of the Treatment period and end of treatment.
In addition:
 - Proportion of patients who have a 1-point improvement or more from baseline
 - Proportion of patients who indicate a severity of 'None'.

Itch-related Quality-of-Life Measures

- Change from baseline in itch-related quality of life at each scheduled weekly visit of the Treatment period (excluding Week 12) and end of treatment, as assessed by the total score of the 5-D Itch Scale.
In addition, at each scheduled weekly visit of the Treatment period and end of treatment:
 - Proportion of patients who either rate the degree of itching intensity over the past 2 weeks as 'Not Present' or the direction of itching as 'Completely Resolved' from the 5-D Itch Scale.
 - Proportion of patients with itching present at each body part and the shift from baseline.
- Change from baseline in itch-related quality-of-life at each scheduled weekly visit (excluding Week 12) of the Treatment period and end of treatment, as assessed by the total score of the Skindex-10 Scale.
- Change from baseline in itch-related quality-of-life at each scheduled weekly visit of the Treatment period and end of treatment with respect to each of the 3 domains of the Skindex-10 Scale.

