Weekly Mean Worst Itching Intensity NRS score	The weekly mean of the 24-hour Worst Itching Intensity NRS score will be defined as the sum of the daily Worst Itching Intensity NRS score reported during a specific week during the Treatment period (eg, Days 1 to 7, Days 8 to 14, Days 15 to 21, etc.) divided by the number of non-missing scores for that week. If there are <4 non-missing daily worst itching scores in a specific week, the corresponding weekly mean worst itching score will be set to missing.
Skindex-10	
Total Scores	Patients will be asked to fill in 1 of 7 circles numbered from 0 (labeled with the anchor phrase “never bothered”) to 6 (labeled as “always bothered”) for each of 10 questions. The total score is the sum of the numeric value of each answered question. For more details see Appendix B.
5-D Itch	
Total Score	Total 5-D Itch score = duration score (single item) + degree score (single item) + duration score (single item) + maximum disability (4 disability items) + category score based on sum of affected body parts. 5-D Itch scores can potentially range between 5 (no pruritus) and 25 (most severe pruritus). For more details see Appendix C

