8.6.2 Analysis of primary efficacy endpoint

The primary efficacy endpoint is defined as the change from baseline to week 12 of the Treatment period with respect to the weekly mean of the daily 24 hour Worst Itching Intensity NRS score. Testing of the primary efficacy endpoint will be 2-sided and conducted at the 5% error level.

The study will be considered positive if at least one safe and efficacious dose is identified. Effectiveness will be evaluated based on results of the primary efficacy analysis either using the estimate of treatment effect or the p-value of the hypothesis tests.

The null hypotheses H_{01} , H_{02} , H_{03} , and H_{04} given below will be tested against the alternative hypotheses H_{A1} , H_{A2} and H_{A3} respectively:

$$\begin{array}{llll} H_{01}: \mu_{D1} - \mu_P = 0, & H_{02}: \mu_{D2} - \mu_P = 0, & H_{03}: \mu_{D3} - \mu_P = 0, & H_{04}: \mu_{D123} - \mu_P = 0 \\ H_{A1}: \mu_{D1} - \mu_P \neq 0, & H_{A2}: \mu_{D2} - \mu_P \neq 0, & H_{A3}: \mu_{D3} - \mu_P \neq 0, & H_{A4}: \mu_{D123} - \mu_P \neq 0 \end{array}$$

Where μ_{D1} , μ_{D2} and μ_{D3} denote the mean change in Worst Itching Intensity NRS score from baseline to week 12 in the three active treatment dose groups and μ_P denotes the mean change from baseline to week 12 in the placebo group (placebo, P). D_1 denotes the CR845 0.25mg dose group, D_2 denotes the CR845 0.5mg dose group and D_3 denotes the CR845 1mg dose group and D_{123} denotes the doses (0.25, 0.5 and 1 mg) combined.

The weekly mean of the 24-hour Worst Itching Intensity NRS score will be defined as the sum of the daily Worst Itching Intensity NRS score reported during a specific week of the Treatment period (eg, Days 1 to 7, Days 8 to 14, Days 15 to 21, etc. till 78 to 84) divided by the number of non-missing scores for that week. If there are <4 non-missing daily worst itching scores during a specific week, the corresponding weekly mean worst itching score will be set to missing. The baseline score will be defined as the average of the daily 24-hour Worst Itching Intensity NRS scores over the last 7 days prior to randomization; at least 4 completed Worst Itching Intensity NRS worksheets will be required prior to randomization.

The primary efficacy variable will be analyzed using a mixed effects model with repeated measures (MMRM). The model will contain treatment, week, and treatment-by-week interaction as fixed effects; baseline score and renal disease status as covariates. For each

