9 CHANGES TO PLANNED ANALYSIS FROM STUDY PROTOCOL

- Antipruritic medications are not identified in the CRF or the database using a Yes/No flag. The use of antipruritic medications will need to be derived based on the indication entered on the CRF. Therefore, a specific analysis of antipruritic medications by ingredient will not be completed since it will not be different than the analysis summarizing medications by preferred term.
- Section 8.6.1 of the protocol defines the primary endpoint as follows: “The weekly mean of the 24-hour Worst Itching Intensity NRS score will be defined as the sum of the daily Worst Itching Intensity NRS score reported during a specific week during the Treatment Period (eg, Days 2 to 8, Days 9 to 15, Days 16 to 22, etc.) divided by the number of days with non-missing scores for that week. If the daily worst itching score is missing for >3 days during a specific week, the corresponding weekly mean worst itching score will be set to missing.”. However, to facilitate patient diary dates anomalies which may result in duplicate dates (e.g. patient completes diary shortly after midnight and then again on same date) and the fact that only the diary date is used for mapping to a specific week as per [section 7.1](#), of this SAP, the underlined text above is replaced with “...divided by the number of non-missing scores for that week. If there are <4 non-missing daily worst itching scores during a specific week...”. In addition, because in this study the Day 1 NRS score is planned to be taken after dosing, weeks are re-defined in this SAP one day earlier than stated in the protocol (eg. Days 1 to 7, Days 8 to 14, Days 15 to 21, etc.).
- Section 8.6.2 of the protocol states that missing Skindex-10 Itch Scale and 5-D Itch Scale total scores will not be imputed. To ensure a more unbiased assessment of these secondary endpoints, which does not ignore missing data, analyses in this SAP state that the same MI method with MAR assumption will be applied to these endpoints in similar fashion to the primary endpoint.

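### The SAP counts the Day 1 itch score in Week 1, although its 24-hour recall reaches back before the first dose; this can dilute the Week 1 treatment difference but does not enter the Week 12 window

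*SAP*

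**What the plan says.** Protocol section 8.6.1 builds the weekly means from windows that begin on Day 2 ("eg, Days 2 to 8, Days 9 to 15, Days 16 to 22, etc"). SAP sections 7.1 and 8.6.2 use windows that begin on Day 1 ("eg, Days 1 to 7, Days 8 to 14, Days 15 to 21, etc. till 78 to 84").

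SAP section 9 discloses the change: "weeks are re-defined in this SAP one day earlier than stated in the protocol". The only reason it gives is the timing of the worksheet: "because in this study the Day 1 NRS score is planned to be taken after dosing".

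Two definitions in the protocol bear on that reason. Section 6.1 fixes the day: "Day 1 of the Treatment Period will be defined as the day of the administration of the first dose of study drug". Section 6.5.1.1 fixes the recall period, since patients are "asked to indicate the intensity of the worst itching they experienced over the past 24 hours".

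SAP section 8.1 treats an efficacy assessment as on-treatment once it follows the first dose. It looks at when the assessment is made, not at the period recalled. A week needs at least four non-missing scores.

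**The concern.** A worksheet dated Day 1 and completed after a Day 1 dose is completed less than 24 hours after that dose. Its recall therefore always reaches into pre-dose hours. Because the item records a maximum, the score cannot fall below the worst itch of those hours, even if the drug works at once. The protocol windows avoid this almost entirely by leaving Day 1 out. The SAP windows bring it in, and no rule or sensitivity analysis takes it out again.

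What is at stake is the Week 1 itch result. SAP section 8.6.4 compares each dose with placebo at every post-baseline week using the MMRM, and section 8.9.2.3 does the same at the interim analysis. Section 4.3 also lists Week 1 responder and complete-responder proportions. No other itch scale is scheduled after baseline before Week 4, so the diary is the only efficacy information on the first weeks. If an early effect exists, the distortion is toward no difference.

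**Working it through.** **Inputs.** Recall of 24 hours (protocol 6.5.1.1). Week 1 is Days 1 to 7, with four to seven usable scores (SAP 7.1, 8.6.2). For scale only, the planning values in protocol 8.2: SD 2.6, effect size 0.52, 60 patients per arm.

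**How much of the Day 1 recall is untreated.** If the score is given h hours after the dose, 24 − h hours are pre-dose. That is more than half whenever h is below 12. To reach h = 12 on the same date, the dose must be taken by noon. The documents give no value for h.

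**How much of the effect Day 1 could carry.** This was illustrated by simulating hourly itch with assumed values: mean 6, SD 1.5, hour-to-hour correlation 0.5 or 0.9, and a full effect straight after the dose. The Day 1 maximum then carries this share of the effect:

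- 4 hours after the dose: 9 to 10%
- 8 hours: 19 to 20%
- 12 hours: 31 to 32%
- 16 hours: 44 to 48%

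A share of one half is therefore a generous case.

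**Dilution of the Week 1 difference.** Let m be the number of scores including Day 1, and f the share of the effect carried by Day 1. The difference is multiplied by (m − 1 + f)/m:

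| Scores m | f = 0 | f = 0.25 | f = 0.5 |
|---|---|---|---|
| 7 | 6/7 = 0.857 | 0.893 | 0.929 |
| 6 | 0.833 | 0.875 | 0.917 |
| 5 | 0.800 | 0.850 | 0.900 |
| 4 | 3/4 = 0.750 | 0.812 | 0.875 |

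The loss is 14% (f = 0) to 7% (f = 0.5) with a full diary, and 25% to 12.5% with four scores. For the treatment difference, Day 1 need not equal baseline. Any drift common to all arms cancels.

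**Scale, using the plan's own figures.** A noncentral t calculation gives 80.7% power for 60 per arm at effect size 0.52, against the stated 80%. For 120 per arm at 0.40 it gives 87.0%, against 86%. So the plan's figures are reproduced, but they concern Week 12; the documents give no Week 1 effect. If the Week 1 effect were also 0.52 × 2.6 = 1.352 points, then with f = 0 a full diary would show 1.352 × 6/7 = 1.16 points and four scores would show 1.352 × 3/4 = 1.01 points. With the SD held at 2.6, power in the full-diary case would be 67.8%. Holding the SD fixed overstates that loss: if Day 1 sat exactly at each patient's baseline mean, the SD of the change would also shrink by 6/7 and the effect size would stay at 0.52. The firm result is the dilution of the estimate, not a power figure.

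**Responders.** With seven scores and Day 1 equal to the baseline mean, a threshold T requires a mean improvement of T × 7/6 over Days 2 to 7. Thresholds of 1, 2, 3 and 4 points become 1.17, 2.33, 3.50 and 4.67.

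**Complete responders.** At least 80% of scores must be 0 or 1, which means 6 of 7, 5 of 6, 4 of 5 or 4 of 4. A Day 1 score above 1 uses the only permitted miss with five to seven scores, and rules out response with four.

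**The case against.** The strongest reply is that little depends on Week 1. No objective concerns onset of effect, and the study is judged on Week 12. The conditional power rule in SAP section 8.9.1 concerns separation from placebo at the end of the study. That stands, and it is why the point is minor.

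A reader might infer that the Day 1 score is simply one more run-in score. The documents do not support this, because no dose-to-score interval is given. Worksheets are completed at home at a similar time each day, so an evening score after a morning dose is possible. What is certain is some pre-dose recall; that most of it is pre-dose holds only below 12 hours.

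A reader might also infer that many Week 1 tests are compromised. SAP sections 8.6.3 and 8.6.4 specify the NRS responder and complete-responder comparisons only at Week 12 and end of treatment. The one specified Week 1 comparison is the MMRM change from baseline.

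The percentages for f = 0 are upper bounds, and 25% also needs exactly three missing days with Day 1 present. Patients enter on a run-in mean of at least 5, so regression to the mean may put Day 1 below baseline in every arm. That would soften the responder thresholds, but it does not remove the dilution of the treatment difference.

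Finally, the SAP's stated reason is not shown to be false, and the change is disclosed. The reason is insufficient rather than wrong: it establishes that the score follows the dose, not that it describes treated time. The shift also has a benefit. Week 12 becomes Days 78 to 84, ending on the planned Day 84 visit, where the protocol's pattern would give Days 79 to 85.

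**Conclusion.** The point holds as a minor one. A Day 1 score given after the dose must include pre-dose time, and the SAP counts it as Week 1 on-treatment data. If there is an early effect, the Week 1 NRS difference is biased toward no difference at both the final and the interim analysis. The bias is up to 14% with seven scores and up to 25% with four, or 7% and 12.5% if Day 1 carries half of the effect. Descriptive Week 1 responder and complete-responder proportions are lowered as well.

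A reader might go further and suppose that the primary result is contaminated. It is not: Day 1 lies outside Days 78 to 84. Week 1 reaches the Week 12 NRS endpoints only as a repeated measure in the MMRM and as a predictor in the imputation. It could also supply the end-of-treatment value for a patient who stops in the first week. The bias does not favour CR845, and Week 1 safety results are untouched.

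**What to change.** Keep Weeks 2 to 12 as the SAP defines them, so that Week 12 stays at Days 78 to 84. Compute Week 1 from Days 2 to 7, still requiring at least four non-missing scores. Apply this to every Week 1 NRS derivation (mean, responder, complete responder) and to the Week 1 variable in the imputation model. State in SAP section 9 that Day 1 is left out because of the 24-hour recall.

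This takes one line in each of SAP sections 7.1 and 8.6.2 and a date condition in the programs. The per-protocol rule in section 6.4 counts weeks by missing days, so it should say how the six-day Week 1 is treated.

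The cost is that Week 1 has at most six scores. A patient with exactly four scores including Day 1 would have only three left, so that Week 1 mean becomes missing and is imputed. The remedy is not perfect: a Day 2 worksheet completed less than 24 hours after the first dose, including one filled in just after midnight, still recalls some pre-dose time.

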11 APPENDICES

Appendix A: Worst Itching Intensity Numerical Rating Scale

This is a representation of the content of the instrument to be used. Please refer to the Study Reference Manual for the instrument to be administered to patients and instructions.

INSTRUCTIONS										
Please indicate the intensity of the WORST ITCHING you experienced over the past 24 hours by marking the box with the number that best describes it. After completing the scale below, please provide your initials in the SUBJECT INITIALS box indicating that you completed the scale by yourself and the DATE and TIME you completed the scale.										
Worst Itching Over the Past 24 Hours										
Please indicate the intensity of the WORST ITCHING you experienced over the past 24 hours.										
0	1	2	3	4	5	6	7	8	9	10
										
NO ITCHING					WORST ITCHING IMAGINABLE					
Date Completed:					Time:			SUBJECT INITIALS		
  D		  M		  M		2	0	  :	  :	First  Middle  Last   
  D		  M		  M		Y	Y	Y	Y	 AM  PM

Statistical Analysis Plan (SAP)

Appendix B: Skindex-10 Scale

This is a representation of the content of the instrument to be used. Please refer to the Study Reference Manual for the instrument to be administered to patients and instructions.

INSTRUCTIONS: During the past WEEK , how often have you been bothered by:							
	0 (Never bothered)	1	2	3	4	5	6 (Always bothered)
1. Your itching							
2. The persistence/reoccurrence of your itching							
3. The appearance of your skin from scratching							
4. Frustration about your itching							
5. Being annoyed about your itching							
6. Feeling depressed about your itching							
7. Feeling embarrassed about your itching							
8. The effects of your itching on your interactions with others (for example: interactions with family, friends, close relationships, etc.)							
9. The effects of your itching on your desire to be with people							
10. The effect of your itching making it hard to work or do what you enjoy							

Date Completed:
 D D M M M M Y Y Y Y

Time: :
 AM PM

SUBJECT INITIALS
First Middle Last

Patients will be asked to fill in 1 of 7 circles numbered from 0 (labeled with the anchor phrase “never bothered”) to 6 (labeled as “always bothered”) for each of the 10 questions. The total score is the sum of the numeric value of each answered question. The total score is subdivided into 3 domain scores, which are sums of the scores of the following questions: disease domain (questions 1 to 3), mood/emotional distress domain (questions 4 to 6), and social functioning domain (questions 7 to 10).

Statistical Analysis Plan (SAP)

